Subjects in Stage 1 and Stage 2 may receive up to 8 cycles of combined therapy until withdrawal of consent, pregnancy, substantial noncompliance with study procedures, intolerable adverse event, documented radiological disease progression or death, principal investigator judgment that it is in the best interest of the subject to stop treatment, or study discontinuation. Subjects, who the principal investigator feels are receiving benefit, may continue to receive additional cycles of therapy following discussions with the Sponsor.

Study Duration:

Each subject should complete all study procedures in approximately 8 months (i.e., screening period up to 14 days; treatment period up to eight 21-day cycles, safety follow-up approximately 30 days after the last dose of study medication). However, for subjects approved to receive additional treatment cycles, the duration may be longer than 8 months. The study duration is estimated at approximately 30 months.

Key Screening Procedures: (key procedures, see Section 7.2 for a complete list):

- Review of inclusion and exclusion criteria
- Medication, cancer history, cancer treatments and medical history
- Vital signs: resting pulse, resting respiration, temperature and resting blood pressure
- Physical examination including height and weight
- ECOG performance status assessment
- Laboratory tests

- Collection of archival paraffin embedded tumor tissue, if available.
- Radiological imaging for disease assessments should be according to RECIST ver. 1.1 as described in Appendix E (within 21 days before enrollment/randomization) and must include an imaging scan (i.e., computerized tomography or magnetic resonance imaging) of the abdomen and pelvis and other site of disease. The imaging modality selected must remain the same throughout the study.

Key Treatment Procedures (key procedures, for a complete list see Sections 7.3, 7.4, and 7.5):

- Record adverse events and concomitant medications
- Resting vital signs and weight
- ECOG performance status assessment
- Laboratory tests
- Blood collection for biomarker assessments (within ± 1 day of the imaging assessment)
- Radiological imaging for a disease assessment every 6 weeks (i.e., at the end of every 2 cycles of combined or single agent therapy)
- Pharmacokinetic sampling (Cycle 1 in Stage 1 only)

Statistical Considerations:

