6.1.2 RX-0201 Dosing Schedule

RX-0201 will be administered on a cyclical basis. For subjects assigned to receive RX-0201 and everolimus, a cycle will be defined as the period elapsing from the first day of RX-0201 administration through Day 21 of the cycle or to the recovery from any adverse events sufficient that a new cycle of therapy can be administered (e.g., on Day 29 or Day 36), whichever occurs later. Once a new cycle starts, the prior cycle is considered to be completed. For subjects assigned to the everolimus only arm, a cycle will be defined as the period elapsing from the first day of everolimus administration through Day 21 of the cycle or to the recovery from any adverse events sufficient that a new cycle of therapy can be administered, whichever occurs later.

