- Turn off the RX-0201 infusion pump, disconnect the infusion bag and record the volume infused during the past 7 days in the subject's medical record and eCRF, if applicable.

7.6 Cycles 1 to n, Days 18-21 – Imaging Assessment – Stage 2

- Disease assessment will occur at the end of Cycles 2, 4, 6, 8, ... n (i.e., after every 6 weeks of therapy).
- Radiological imaging to assess disease extent. Radiological assessment must include CT scan or MRI of the abdomen and pelvis and the modality selected should be the same throughout the study. The results of the imaging assessment must be available

and reviewed before the start of the next cycle. Some imaging assessments may be collected for a second review by a central imaging vendor.

- Disease assessment should be conducted according to the RECIST ver. 1.1 guidelines modified as described in Appendix E.
- Blood collection for biomarker sample analysis within 1 day of tumor assessment

7.7 Unscheduled Visit(s) – Stage 1 and Stage 2

An unscheduled visit may be performed at any time during the study at the request of the subject or as deemed necessary by the investigator. The date and reason for the unscheduled visit will be documented in the subject's medical record and eCRF, as well as any other data obtained (e.g., adverse events, concomitant medications and treatments, and results from procedures or tests).

7.8 End of Treatment or Early Termination Visit - Stage 1 and Stage 2

The following procedures will be performed:

- Record concomitant medication(s)
- Record adverse event(s). Serious adverse events will be reported immediately. Any adverse event that is considered related to study drug(s) will be followed to resolution or return to baseline.
- ECOG performance status
- Vital signs: resting pulse, resting respiration rate, resting blood pressure (i.e., after the subject has been seated for at least 5 minutes) and temperature measurements.
- Everolimus compliance – Record the number of tablets taken at home since the last visit.
- Laboratory tests
 - Urinalysis
 - Hematology panel
 - Chemistry panel
 - Coagulation
 - Pregnancy test (if applicable, urine or serum)

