9.2 Study Endpoints, Subsets, and Covariates

9.2.1 Study Endpoints

9.2.1.1 Primary Endpoints

- Incidence of adverse events and clinical laboratory abnormalities defined as dose-limiting toxicities (Stage 1)
- Progression free survival at 4.5 months (Stage 2)

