### **Progression-Free Survival (PFS)**

Progression-free survival will be defined as the time from date of initiation of treatment until the earlier of either first documented tumor progression (PD) or death from any cause. Subjects alive without progression or lost to follow-up at the time of analysis will be censored at the date of last response assessment. Progression free survival will be analyzed at 4.5 months (Stage 2).

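### Stage 2 scans follow cycle number, so about two weeks of accumulated cycle delay puts the third scan at or past the 4.5-month landmark and modestly inflates the primary PFS estimate

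*Protocol*

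**What the plan says.** - **Scan timing.** Protocol 7.6 places Stage 2 imaging on Days 18-21 and states "Disease assessment will occur at the end of Cycles 2, 4, 6, 8, ... n". The Synopsis (Key Treatment Procedures) asks for "Radiological imaging for a disease assessment every 6 weeks" and equates this with the end of every two cycles. No text fixes a scan to calendar time from first dose.
- **Cycle length.** Under Protocol 6.1.2 a cycle runs through Day 21, and is extended if need be "to the recovery from any adverse events sufficient that a new cycle of therapy can be administered (e.g., on Day 29 or Day 36". Section 6.6.2 delays the next cycle a week at a time and states no maximum.
- **Endpoint.** The Stage 2 primary endpoint is "Progression free survival at 4.5 months (Stage 2" (Protocol 9.2.1.1), repeated in SAP 4.3. PFS runs from first dose (Protocol 9.5.2.3).
- **Dating of events.** The censoring table in SAP 9.1.1 dates progression at the assessment that showed it. SAP 7.1 defines no analysis window. Neither document converts 4.5 months to days.

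**The concern.** Two cycles equal six weeks only if no cycle is extended. The endpoint is read at a calendar time, but the scans that supply it drift with toxicity. If enough delay accumulates, the last scan before the landmark is the Cycle 4 scan. Subjects who progressed after it are then counted as progression-free at 4.5 months.

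For subjects whose third scan is late, the error favours the drug and comes from its poor tolerability. Randomization has been dropped and only about 3 everolimus-alone subjects are expected (Protocol 3.3). The combination estimate will therefore be read largely on its own, with no useful concurrent control sharing the same error.

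**Working it through.** **1. The plan's own figures.** 2 cycles x 21 days = 42 days = 6 weeks, which is correct when there is no delay. Protocol 9.3 gives maximum 90% half-widths of ±0.28 (n = 10) and ±0.20 (n = 20). Exact Clopper-Pearson limits at a proportion of 0.5 give 0.278 and 0.198, so both reproduce. They refer to 9-month PFS and serve here only as a yardstick.

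**2. Landmark.** 4.5 x 30.4375 = 136.97, so about Day 137. At 30 days per month it is Day 135.

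**3. Third-scan day** = 5 x 21 + (18 to 21) + total delay at the starts of Cycles 2 to 6. A start on Day 29 is a 7-day delay, and a start on Day 36 is a 14-day delay.

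| Total delay | Third scan | Against Day 137 |
|---|---|---|
| 0 | Day 123-126 | before |
| 7 days | Day 130-133 | before |
| 14 days | Day 137-140 | at or past |
| 21 days | Day 144-147 | past |

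Two one-week delays, or one cycle start moved to Day 36, reach 14 days.

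**4. What the estimate returns.** Assume exponential PFS with the medians in Protocol 9.3 (m = 9 or 4.5 months), so S(t) = 2^(-t / (m x 30.4375)). If every event is dated at the next scan, the 4.5-month estimate equals S at the last scan on or before the landmark.

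| Last scan by landmark | m = 9 | m = 4.5 |
|---|---|---|
| True value, Day 137 | 0.707 | 0.500 |
| Day 126 (no delay) | 0.727 | 0.529 |
| Day 133 (7 days late, still in time) | 0.714 | 0.510 |
| Day 98 (third scan late, second 14 days late) | 0.780 | 0.609 |
| Day 84 (third scan late, second on time) | 0.809 | 0.654 |

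With no delay the excess is 0.727 - 0.707 = 0.020, or 0.529 - 0.500 = 0.029. This is the off-grid part. A single one-week delay lowers the estimate slightly.

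**5. Averaging over subjects.** The delay rate is an assumption: each of the five cycle starts is delayed with probability p, two-thirds of the time by 1 week and one-third by 2 weeks. Weighting all 3^5 = 243 delay patterns, with scans on Day 21, gives:

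| p | Third scan late | m = 9 (added by delay) | m = 4.5 (added by delay) |
|---|---|---|---|
| 0 | 0% | 0.727 | 0.529 |
| 10% | 19% | 0.736 (+0.009) | 0.542 (+0.014) |
| 20% | 40% | 0.747 (+0.020) | 0.559 (+0.031) |
| 30% | 59% | 0.757 (+0.030) | 0.575 (+0.046) |

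Spreading scans evenly over Days 18-21 and counting elapsed days from first dose gives 16-53% late for p of 10-30%. Delay then adds 0.006-0.025 (m = 9) or 0.009-0.038 (m = 4.5). With one-week delays only, at p = 10%, 8% of third scans are late and the m = 9 estimate is 0.728, almost unchanged from 0.727.

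**The case against.** The case against has substance.

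- **Not every event waits for a scheduled scan.** SAP 9.1 evaluates subjects when symptoms suggest progression, Protocol 7.8 includes a tumor assessment at end of treatment, and deaths count on their own date. If 30% of events (an assumption) are dated exactly, the worst case above becomes 0.70 x 0.757 + 0.30 x 0.707 = 0.742. On schedule it would be 0.70 x 0.727 + 0.30 x 0.707 = 0.721. The part due to delay falls from 0.030 to 0.021. This stands, so the tabled figures are upper ones.
- **The delay rate may be low.** Protocol 6.7 lets RX-0201 stay on schedule when everolimus toxicity is the cause, and Section 2.3.2 reports mostly mild or moderate events in the first stage. This stands; the true rate is unknown.
- **Scan day matters.** A Day 18 scan after a 14-day total delay is 136 elapsed days from first dose, just inside the landmark at 137 days. This also stands.
- **The protocol already plans six-weekly Kaplan-Meier landmarks** (9.5.2.3). Weeks 18 and 24 bracket 4.5 months. This helps, but week 18 is Day 126, which a third scan delayed by one week already misses.
- **No decision rule depends on the estimate.** Stage 2 seeks preliminary estimates, and 0.01-0.03 is 0.2-0.6 of one subject in 20. That limits the importance. It does not remove an error that grows with the share of late scans.

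A reader might infer that any delay raises the estimate, or that more toxicity always means higher PFS. Step 4 shows otherwise for one week. A reader might also attribute the whole gap between 0.542-0.575 and the true 0.500 to delay. Of that gap, 0.029 is present with no delay at all.

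**Conclusion.** The point holds as a modest upward bias in the primary Stage 2 estimate. About 14 days of total delay over Cycles 1 to 5 puts the third scan at or past 4.5 months, and nothing in either document prevents or adjusts for it.

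Under an assumed 10-30% chance of delay per cycle, about 16-59% of third scans are late, depending on scan day. Delay adds about 0.01-0.03 at a 9-month median and 0.01-0.05 at a 4.5-month median. These figures rest on exponential PFS, scan-only detection and the assumed rate, and the routes to earlier detection reduce them. The further 0.02-0.03 from the off-grid landmark is separate, and calendar scanning would leave it in place.

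The documents do not support reading this as invalidating the estimate: the effect is small beside ±0.20. It is worth correcting because it is systematic, linked to tolerability and cheap to remove.

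**What to change.** **Protocol.** Reconcile the Synopsis, Section 7.6 and Section 6.1.2 so that efficacy scans stay at the protocol's own 6-week calendar intervals from first dose, with a stated window, whether or not a cycle is delayed. Dosing and delay rules stay as they are. The requirement in 7.6 that results be reviewed before the next cycle must be made consistent with this timing.

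**SAP 9.1.1.**
- Define 4.5 months in days.
- Report the actual third-scan day and the number of subjects scanned after the landmark.
- Add an interval-censored (Turnbull) PFS estimate as supportive only, with its interpolation rule stated. On a 42-day grid the estimate is not determined between Day 126 and Day 168, where Day 137 lies.
- Read these beside the week-18 and week-24 Kaplan-Meier estimates already planned.

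**Cost.** A protocol clarification and a short SAP addition; the SAP steps use dates already collected. A delayed subject may have a scan mid-cycle, and one whose delays add up to about 6 weeks may need one more scan. The 4.5-month estimate may come out slightly less favourable.

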6.6.1 RX-0201 Dose Modifications During a Cycle

If a subject experiences a RX-0201-related DLT (as defined in Section 6.5), SAE, or other intolerable adverse event and requires a dose reduction, RX-0201 administration should be interrupted, as necessary, until the adverse event resolves or stabilizes to an acceptable degree (generally to the pretreatment severity grade). If appropriate, more frequent laboratory monitoring may be instituted until abnormalities have recovered to the pretreatment severities. Thereafter, RX-0201 may be reinstated, but the dose of RX-0201 for the remainder of that cycle should be reduced by 1 dose level. Successive adjustments to progressively lower dose levels can be made. If the subject cannot tolerate RX-0201 at Dose Level 1 (125 mg/m²/day) then the subject should be discontinued from RX-0201 therapy.

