6.6.2 RX-0201 Dose Modifications at the Beginning of the Next Cycle

A new cycle of RX-0201 treatment may begin no earlier than Day 1 of the new cycle but should be delayed, as necessary, until adverse events or laboratory abnormalities have returned to baseline levels. If adverse events or laboratory abnormalities are not resolved to baseline, week-by-week delays in initiating the new cycle of treatment should be instituted. Once all toxicities have returned to baseline, the next cycle of therapy can be initiated.

Subjects experiencing any of the DLTs described in Section 6.5 in the current cycle of therapy should have the dose in the next cycle of therapy reduced by 1 dose level. Subjects who required an intra-cycle dose reduction, during the current cycle of therapy, should have the dose in the next cycle of therapy administered at no higher than the highest dose tolerated in the current cycle. Successive inter-cycle adjustments to progressively lower dose levels can be made. If the subject cannot tolerate RX-0201 at Dose Level 1 (125 mg/m²/day) then the subject should be discontinued from RX-0201 therapy.

Subjects in Stage 1 will receive additional cycles at the same dose to which they were assigned in Cycle 1.

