- Resting vital signs: pulse, respiration rate, blood pressure (i.e., after the subject has been seated for at least 5 minutes) and temperature measurements.
- Blood sample for RX-0201 pharmacokinetics will be collected:
 - Immediately prior to the end of RX-0201 infusion
- Turn off the RX-0201 infusion pump, disconnect the infusion bag and record the volume infused during the past 7 days in the subject's medical record and eCRF.
- Blood sample for RX-0201 pharmacokinetics will be collected:
 - 1 hour \pm 5 minutes, 2 hours \pm 5 minutes, 3 hours \pm 10 minutes, 4 hours \pm 10 minutes, and 6 hours \pm 10 minutes after the infusion pump has been turned off.

7.3.9 Cycle 1 Day 16 - Stage 1

- Recording of concomitant medication(s)
- Recording of adverse event(s). Serious adverse events will be reported immediately. Any adverse event that is considered related to study drug will be followed to resolution or return to baseline.
- Resting vital signs: pulse, respiration rate, blood pressure (i.e., after the subject has been seated for at least 5 minutes) and temperature measurements.
- Blood sample for RX-0201 pharmacokinetics will be collected:
 - 24 hours \pm 1 hour after the infusion pump has been turned off on Cycle 1 Day 15.
- Everolimus (10 mg) will be taken orally (for details see Section 6.1.1) at the clinic. The time of the dosing will be recorded.

7.3.10 Everolimus Dosing – Cycle 1 Days 17 to 21 - Stage 1

Everolimus (10 mg) will be administered orally at home (for details see Section 6.1.1) each day.

7.4 Treatment Period - Cycles 2 to n – Stage 1

Subjects who complete Cycle 1 in Stage 1, and for whom the principal investigator feels may benefit from additional treatment cycles, may continue to receive additional cycles of RX-0201 plus everolimus therapy and will follow the treatment procedures and assessments outlined in Sections 7.5 and 7.6 starting at Cycle 2 Day 1. Otherwise, an End of Treatment visit should be completed.

7.5 Treatment Period - Cycles 1 to n – Stage 2

7.5.1 Pre-dosing Assessments - Cycles 1 to n, Day 1 - Stage 2

The following procedures will be performed within 5 days **before** the administration of any study treatment unless otherwise described:

- Record concomitant medication(s) (Cycles 1 – 16 only)
- ECOG performance status
- Weight measurement

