9.5.2.2 Laboratory Safety Data

All hematology, chemistry, coagulation and urinalysis will be listed by treatment group and subject. Where normal ranges are available, values outside of the range will be flagged. The data will be summarized by treatment group using standard descriptive statistics at each of the scheduled time point in the study. For continuous parameters, a summary of the changes from baseline to each post dose laboratory assessment will also be produced for each treatment group.

Shift analysis for selected laboratory parameters between baseline and both the final visit worst-case on-study value will be summarized according to NCI CTCAE version 4.03 toxicity grades.

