### **7.1 Timing of Analyses**

Analysis window is not defined in this study.

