### **8.13 Clinical Laboratory Evaluations**

Abnormal laboratory values will be assessed according to NCI CTCAE v4.03 where possible. The criteria for “clinically significant” laboratory abnormalities include a laboratory abnormality that leads to a DLT or a laboratory abnormality that results in any treatment-emergent therapeutic intervention (i.e., concomitant medication or therapy), or any other laboratory abnormality judged by the investigator to be of other particular clinical relevance.

All relevant clinical laboratory tests will be classified as Low, Normal, and High, or Normal/Abnormal according to the normal ranges. This categorical data will be summarized in shift tables comparing the results at each scheduled post-baseline visit with those at the baseline visit.

When there are multiple values within a visit for a particular laboratory variable, the worst value will be taken (worst being the smallest value for criteria below a certain threshold or the largest value for criteria above a certain threshold). If a subject has both a value below the threshold and a value above the threshold, the value furthest from the threshold will be chosen.

Urinalysis data will be presented in subject listings only.

All laboratory (hematology, coagulation, clinical chemistry, and urinalysis) parameters, values, units, normal range, flags collected (normal/abnormal) in the clinical database will be included in by-subject listings for further medical review. Laboratory values with associated CTCAE version 4 grades will have the associated grade displayed.

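### SAP 8.13 gives laboratory results from unscheduled visits no place in its laboratory tables and omits the protocol's worst-case CTCAE-grade shift, while SAP section 11 reports no changes

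*Protocol*

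**What the plan says.** **Collection.** Protocol 7.7 allows an unscheduled visit at any time, at the subject's request or on the investigator's judgement, and sends its findings to the medical record and eCRF, "as well as any other data obtained (e.g., adverse events, concomitant medications and treatments, and results from procedures or tests". Protocol 6.6.1 adds that after an RX-0201-related toxicity "more frequent laboratory monitoring may be instituted until abnormalities have recovered to the pretreatment severities".

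**SAP tables.** SAP 8.13 classifies results as low, normal or high (or normal/abnormal) and continues: "This categorical data will be summarized in shift tables comparing the results at each scheduled post-baseline visit with those at the baseline visit". SAP 7.1 reads: "Analysis window is not defined in this study". SAP 8.13 has one rule for repeated values: "When there are multiple values within a visit for a particular laboratory variable, the worst value will be taken". Every laboratory value in the database goes into by-subject listings, with its CTCAE grade where one applies.

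**Protocol tables.** Protocol 9.5.2.2 summarises laboratory data "using standard descriptive statistics at each of the scheduled time point in the study". It then adds a second analysis for selected parameters: a shift by CTCAE grade from baseline to the final visit and to the worst-case on-study value. (The sentence seems to lack a conjunction; I read it as both.) Nothing in that sentence confines the worst case to scheduled visits.

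**Changes.** Protocol 9.5.1 requires the SAP to describe any change from the protocol's analyses. SAP section 11 declares none.

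**The concern.** Changes in clinical laboratory tests over time are a secondary endpoint in both stages. An unscheduled sample is usually drawn because something looks wrong or a known toxicity is being followed. Leaving such results out of the laboratory tables selects on the outcome, and the error runs towards showing no laboratory effect.

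The issue is realistic for this drug. Protocol 2.3.2 names thrombocytopenia among the most common toxicities attributed to the combination in Phase 1b, and among those related to RX-0201 when given with gemcitabine. One dose-limiting toxicity in protocol 6.5 depends on severe neutropenia persisting for at least 3 days, which cannot be judged from counts about 21 days apart. The protocol thus relies on extra sampling, and the SAP then gives those samples no place in its tables.

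**Working it through.** The plan gives no figure on this point to reproduce. The check sets the schedule, the SAP rules and the protocol analysis side by side.

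**1. When scheduled panels fall.** Inputs: protocol 7.3.1, 7.5.1 and 7.8, and Appendices A and B. Panels are listed at screening, Day 1 of each cycle and the end-of-treatment or early-termination visit. None is listed for Day 8 or Day 15.
- Over the planned 8 cycles (8 × 21 = 168 days) there are 8 pre-cycle panels. The first is pre-dose, leaving 8 − 1 = 7 post-baseline panels plus the end-of-treatment panel.
- The infusion occupies the first 14 days of a cycle. The next panel may be drawn up to 5 days before Day 1 (7.5.1, Appendix B), or up to 3 days before (Appendix A). With no delay, its earliest time is 21 − 5 = 16 days (or 21 − 3 = 18 days) after the infusion starts.
- That is 16 − 14 = 2 days (or 18 − 14 = 4 days) after the infusion ends at the earliest, and 21 − 14 = 7 days at the latest.
- Once an infusion has started, no scheduled panel falls within it unless an end-of-treatment or early-termination visit happens to. Other values from that period can come only from unscheduled testing.

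**2. Does the scheduled panel depend on recovery?** Protocol 6.6.2 postpones the next RX-0201 cycle, week by week, "until adverse events or laboratory abnormalities have returned to baseline levels". A delay moves Day 1, so the Day 1 panel tends to sit nearer to recovery than samples taken mid-cycle.

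**3. Can an unscheduled result enter an SAP laboratory table?** The shift table needs a scheduled visit. A window could assign an off-schedule result to such a visit, but none is defined. The worst-value rule chooses among values already assigned to one visit, so it cannot do the assigning. No route is stated.

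**4. Other routes in the SAP.**
- *Adverse-event tables (SAP 8.10).* An abnormality counts if it needs intervention, leads to investigation beyond a confirmatory repeat, or leads to interruption or discontinuation of study drug, unless it belongs to a clinical event already reported. Abnormalities below that threshold are expressly not adverse events and are left to general laboratory monitoring. The laboratory tables are where they would have to be summarised.
- *Dose-limiting toxicity table (SAP, Safety Analyses; 5.5.1).* Cycle 1 only, and only events judged related to RX-0201.
- *By-subject listings.* Complete, but not a summary.

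**5. The protocol's route.** The worst-case shift in protocol 9.5.2.2 could take in unscheduled values. The SAP specifies shift tables only against normal ranges (8.13 and the opening of Safety Analyses). SAP 8.13 does say that abnormal values are assessed by CTCAE, but the listing is the only output there that it says will display a grade. The worst-case shift is therefore absent, and section 11 does not say so.

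**The case against.** The strongest reply is that these values are not lost.

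- The protocol already plans a worst-case shift, and the SAP has not declared it dropped.
- Abnormalities with clinical consequences reach the adverse-event tables by maximum severity. The extra monitoring in protocol 6.6.1 follows a dose-limiting toxicity, a serious event or an intolerable event, so that event is already counted. Cycle 1 dose-limiting toxicities are tabulated separately.
- The recovery argument is a tendency only. A pre-cycle panel may itself be abnormal and trigger the delay. If repeats are filed under that same visit, the worst value is taken. Section 6.6.2 concerns RX-0201 cycles, and under 6.7 RX-0201 may continue on schedule when the toxicity is due to everolimus. End-of-treatment panels do not wait for recovery.
- The study is small, its safety analysis is descriptive, and every value is listed.

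Much of this stands. A reader might infer that the abnormal values appear in no summary at all. The documents do not support that: the adverse-event and dose-limiting toxicity tables take in part of them, and the protocol's worst-case shift could take in more. Nor is it right that the values which prompted extra testing are always missing. A prompting value may come from a scheduled panel and then sits in the shift table. The results at risk are those obtained at the unscheduled visit. The point also does not carry over to vital signs, for which neither document plans a worst-value analysis.

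Two things remain. Unscheduled abnormalities below the adverse-event threshold, or attached to an event already reported, have no place in an SAP summary of laboratory data. And the protocol's worst-case shift does not answer the concern, because the SAP leaves out the one table that would have covered the gap.

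**Conclusion.** The point holds for the laboratory summaries that the SAP specifies. Results from unscheduled visits enter none of them, and the protocol's worst-case CTCAE-grade shift has been omitted without being declared. The likely direction is an understatement of laboratory toxicity for a secondary endpoint in both stages.

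The size cannot be estimated. The documents do not say how many subjects would have abnormalities seen only at unscheduled visits, and any number put forward would simply return its own assumption. The Stage 1 primary endpoint is not affected, since SAP 4.3 identifies dose-limiting toxicities through the adverse-event dataset.

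The conclusion assumes that the tables are programmed as SAP 8.13 is worded. Table shells are not in the documents and SAP section 13 lists figures only, so this could not be checked.

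**What to change.** In SAP 8.13:

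1. Restore the protocol 9.5.2.2 table of shift from baseline to worst on-study value by CTCAE grade, and name the selected parameters.
2. State that it uses every result after first dose, scheduled or unscheduled.
3. State that the by-visit tables use nominal scheduled visits only.

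If the worst-case table was dropped on purpose, declare and explain that in SAP section 11 instead of reporting no changes.

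The cost is a few sentences and one table on data already collected. There is one small drawback: subjects tested more often have more chances of an extreme value, which a footnote to the table can state. No change to the testing schedule is needed.
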